5.4.2.1 Progression-free Survival

DEFINITION

PFS is defined as the time from the date of randomization to the date of first documentation of disease progression based on investigator assessments or date of death, whichever occurs first.

Determination of the date of PFS event or censoring is summarized in Table 5 below.

Table 5 PFS Event and Censoring Rules

No.	Situation	Date of Progression or Censoring	Outcome
1	No baseline or postbaseline adequate tumor assessments	Date of randomization	Censored
2	Progression documented between scheduled visits, on or prior to new anticancer therapy [#] and within 28 days after the last dose of study treatment	Date of first radiologic PD assessment	PFS Event
3	No progression at the time of data cutoff	Date of last adequate radiologic assessment on or prior to data cutoff	Censored
4	New anticancer therapy started	Date of last adequate radiologic assessment on or prior to the start of new anticancer therapy	Censored
5	Death before first PD assessment, on or prior to start of new anticancer therapy [#] and within 28 days after the last dose of study treatment	Date of death	PFS Event
6	Death between adequate assessment ^{#,*}	Date of death	PFS Event
7	Death or progression after more than one missed visit/tumor assessment ^{**}	Date of last adequate radiologic assessment before missed tumor assessments	Censored
8	Death or progression after 28 days from the last dose of study treatment	Date of last adequate radiologic assessment before the date of last dose of study treatment + 28 days	Censored
9	No progression and treatment discontinuation for reasons other than PD	Date of last adequate radiologic assessment before treatment discontinuation (ie, within last dose date + 28 days)	Censored

Note:

If documented PD and/or death occurs after the last dose, it is counted as a PFS event as long as the PD and/or the death occurs within 28 days since the date of the last dose of study treatment and provided that it does not violate other censoring rules (eg, start of new anticancer therapy before the PD or death). Otherwise the subject will be censored on the date of the last tumor assessment before the date of last dose of the study treatment.

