* Adequate tumor assessment is radiologic assessment of CR, PR, SD, non-CR/non-PD or PD as determined by investigators at regular interval as defined in the protocol. Any tumor assessments after new anticancer therapy starts or after 28 days from the last dose date will not be considered in the definition of PFS.

** More than one missed visit/adequate tumor assessment is defined as having the duration between two consecutive tumor assessments or the duration between the last adequate tumor assessment and death/PD being longer than (>) 118 days (the visit schedule for tumor assessment is during every 8th week for this study).

The priority of the censoring rules is described as follows:

1. If the subject had PD or death, the following sequence will be applied:

- If a subject did not have baseline or postbaseline adequate tumor assessments (No. 1), the subject will be censored at the date of randomization. However, if the subject died within 118 days after randomization and did not receive any new anticancer therapy, it will be counted as a PFS event at the date of death. If a subject had new anticancer therapy before PD or death (No. 4), the subject will be censored at the date of the last adequate tumor assessment on or prior to the date of new anticancer therapy. If PD is reported after the date of the last dose + 28 days, the subject will be censored at the date of last tumor assessment before the date of last dose + 28 days (No. 8). If PD or death happened within 28 days after the last dose date, it will be considered as a PFS event.
 - If a subject missed two or more tumor assessments before PD or death (No. 7), the subject will be censored at the date of the last adequate tumor assessment before the missed tumor assessments. Note that if a subject is censored by both of this criterion and start of new anticancer therapy criterion, the earliest censoring date will be used.
 - Otherwise, if a subject had PFS event (No. 2, No. 5 or No. 6), the earliest event date will be used.
2. If a subject did not have PD or death, the censoring date will be the earliest censoring date if the subject met multiple censoring criteria (No. 1, No. 3, No. 4, No. 7).

ANALYSIS METHOD

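### SAP 5.4.2.1 states the PFS missed-scan censoring rule inconsistently and too broadly, so clear scans after a gap, and a later well-dated event, can be discarded

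*SAP*

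**What the plan says.** All the relevant text is in SAP 5.4.2.1.

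- **Table 5, No. 7.** The situation is "Death or progression after more than one missed visit/tumor assessment". The date used is "Date of last adequate radiologic assessment before missed tumor assessments", and the outcome is censored.
- **Double-asterisk note to Table 5.** More than one missed assessment means "having the duration between two consecutive tumor assessments or the duration between the last adequate tumor assessment and death/PD being longer than" a limit of 118 days. The reason given is that "the visit schedule for tumor assessment is during every 8th week for this study".
- **Priority rule 1 (subjects with an event).** The text starts "If a subject missed two or more tumor assessments before PD or death (No. 7), the subject will be censored at the date of", and the date meant is that of the adequate scan preceding the missed ones. The final bullet, which counts the event, starts from the position that this did not apply. An earlier bullet in the same list says, without qualification, that PD or death within 28 days of the last dose is an event.
- **Priority rule 2 (event-free subjects).** The instruction is that "the censoring date will be the earliest censoring date if the subject met multiple censoring criteria (No. 1, No. 3, No. 4, No. 7").
- **Table 5, No. 3 (no progression at cutoff).** Censor at "Date of last adequate radiologic assessment on or prior to data cutoff".

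The other note under Table 5 makes the 28-day allowance for events after the last dose conditional on the other censoring rules. SAP 5.8.1 analyses PFS by independent imaging review in the same way as investigator PFS.

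**The concern.** Censoring after missed scans is useful when PD or death directly follows the gap, because the true progression date may lie anywhere within it. Once an adequate scan after the gap shows no progression, that uncertainty is gone: the subject is known to have been progression-free up to that scan, and a later PD found on schedule is well dated.

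The note's first limb, a gap between any two consecutive assessments, does not make this distinction, and nothing resets the rule when scans resume. Priority rule 1 asks only that the missed scans come before the event, not immediately before it. Priority rule 2 carries an event-only rule over to subjects with no event. Documented follow-up, and sometimes a valid event, can therefore be dropped from the Kaplan-Meier estimates and the hazard ratio. Two programmers working from the table and from the priority list could also build different PFS datasets. The planned PFS sensitivity analyses change only the analysis set, so none of them would show the effect.

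**Working it through.** **1. The 118-day limit.** Input: one scan during every 8th week from randomization (the note; also SAP 8.1). Taking the window as the seven days of that week, scans fall on days 50–56, 106–112, 162–168 and 218–224.

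| Scans missed in between | Shortest gap (days) | Longest gap (days) |
|---|---|---|
| 0 | 106 − 56 = 50 | 112 − 50 = 62 |
| 1 | 162 − 56 = 106 | 168 − 50 = 118 |
| 2 | 218 − 56 = 162 | 224 − 50 = 174 |

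The plan's figure reproduces: 2 × 56 + 6 = 118 is the longest gap with one missed scan, so a gap over 118 days means two or more were missed. The threshold is sound. The problem is where the rule applies.

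**2. Worked example.** Take a subject on treatment throughout, with no new anticancer therapy. Scans are done at weeks 8 and 16 and missed at weeks 24 and 32. A clear scan follows at week 40, then clear scans every 8 weeks, with PD at week 80.

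- Gap: (40 − 16) × 7 = 168 days, which exceeds 118, so the note's first limb is met.
- Priority rule 1, No. 7: censored at week 16, day 112.
- No. 7 limited to a gap immediately before the event: the last interval is 56 days, so PD counts at week 80, day 560.
- Difference: 560 − 112 = 448 days (64 weeks) and one event.

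**3. The same subject without PD, last clear scan at week 80.** No. 3 gives day 560 and No. 7 gives day 112. Priority rule 2 takes the earlier, day 112. Whenever scans resume after a gap, the No. 7 date is earlier than the No. 3 date, so No. 7 overrides it. Priority rule 2 also omits No. 9, which Table 5 does write for subjects without progression. The list and the table therefore disagree in both directions.

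**4. How many subjects.** The documents give no missed-scan rate. A single-arm simulation compared the any-gap reading with the limited rule. Its assumptions, none from the documents, are exponential PFS with median 9 or 14 months, follow-up uniform over 6 to 30 months, and each scan missed independently. Treatment discontinuation and new therapy were not modelled.

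| Median PFS (months) | Chance a scan is missed | Records changed | Events per 306: limited rule | Events per 306: any gap | Mean days lost per changed record |
|---|---|---|---|---|---|
| 9 | 2% | 0.12% | 211.5 | 211.4 | 355 |
| 9 | 5% | 0.62% | 209.6 | 208.8 | 349 |
| 9 | 10% | 2.68% | 205.9 | 202.5 | 351 |
| 9 | 15% | 5.43% | 200.7 | 193.8 | 355 |
| 14 | 2% | 0.15% | 167.1 | 167.0 | 374 |
| 14 | 5% | 0.92% | 164.9 | 164.1 | 357 |
| 14 | 10% | 3.50% | 161.0 | 157.7 | 372 |
| 14 | 15% | 7.36% | 155.8 | 149.3 | 376 |

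About 0.1% to 7.4% of records change, and 0.1 (211.5 − 211.4) to 6.9 (200.7 − 193.8) events are lost per 306 subjects. In every row, more than half of the changed records had no counted event even under the limited rule.

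**The case against.** Two textual arguments deserve an answer.

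- *No. 7 cannot apply to event-free subjects.* Table 5 restricts it to death or progression, so its entry in priority rule 2 could be treated as inert, leaving No. 3 to govern. This shows a real conflict but does not remove it: naming No. 7 in a rule for subjects without PD or death has an effect only if it applies to them.
- *The event is counted before No. 7 is reached.* Read in sequence, the 28-day sentence in the first bullet of priority rule 1 would make the example's on-treatment PD an event. That reading is available. Against it, the note under Table 5 makes such events subject to the other censoring rules, and the final bullet counts an event only if No. 7 has not applied. The sentence also does nothing for event-free subjects.

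So it stands that the text is inconsistent, not that it has a single fixed meaning.

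A reader might also infer three stronger things that the documents do not support.

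- *That the censoring would differ between arms*, because toxicity leads to missed scans. Scans are timed from randomization (Protocol Table 6), visits continue during treatment holds (Table 6, footnote b), and interruptions over 28 days need sponsor approval (Protocol Table 2, note a). A difference is possible, but nothing shows one.
- *That the main secondary endpoint is damaged.* The documents do not rank PFS above the other secondary endpoints, and SAP 5.3.3 says none of them is formally tested.
- *That a definite number of records would be wrong.* No missed-scan rate is given.

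**Conclusion.** The missed-scan rule is wrong as written and should be corrected. On the better reading, one early gap over 118 days censors a subject before that gap, whatever clear scans or event follow; in the example this costs 448 days and one event. That reading rests on the Table 5 notes and the order of the priority list. The 28-day sentence supports another reading for subjects with an event, which is itself a reason to reconcile the text.

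The consequences are limited to the descriptive secondary PFS results (Kaplan-Meier estimates and hazard ratio) and the exploratory PFS by independent imaging review. The ORR at 24 weeks and the primary safety test are unaffected. The share of subjects affected is unknown and may be negligible; the 0.1% to 7.4% range depends wholly on the simulation's assumptions.

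**What to change.** In SAP 5.4.2.1:

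1. Limit No. 7 and its note to a gap of more than 118 days immediately preceding PD or death.
2. State that a later adequate scan without PD restores follow-up.
3. Remove No. 7 from priority rule 2, so that subjects without PD or death are censored at the last adequate assessment under the other rules. Check at the same time whether No. 9 belongs in that list.
4. State that the 28-day sentence in priority rule 1 is subject to No. 7 as so limited.

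The cost is a few lines of SAP text and a small change to the PFS derivation, which carries over to the PFS by independent imaging review. No new data are needed, and the 118-day threshold stays.

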5.4.2.2 Objective Response Rate

ORR is defined as the proportion of subjects achieving a best overall response of confirmed CR or PR during treatment or within 28 days after the last dose date but on or prior to the start of new anticancer therapy at the time of clinical data cutoff. Subjects with overall responses achieved after the start of new anticancer therapy or after 28 days from the last dose date will not be considered as responders. Subjects who do not have a tumor response assessment for any reason will be considered non-responders and will be included in the denominator when calculating the response rate.

The point estimate of ORR and corresponding 95% CI based on asymptotic normal approximation will be summarized for each treatment arm. Odds ratio with 90% CI will be estimated using the CMH method stratified by MSKCC prognostic group and prior PD-1/PD-L1 treatment. In addition, the treatment difference in ORR between lenvatinib 14 mg and lenvatinib 18 mg will also be estimated along with 90% CIs based on the asymptotic

normal approximation.

A sensitivity analysis of ORR based on the Per-Protocol Analysis Set 2 and Full Analysis Set will be performed in a similar manner as described above.

In addition, waterfall plot for the percentage changes from baseline to postbaseline nadir (ie, best percentage changes from baseline) in sum of diameters of the target lesions will be presented. The depth of response for $>0\%$, $\geq 30\%$, $\geq 50\%$ and $\geq 75\%$ maximum reduction in sum of diameters will be summarized.

5.4.2.3 Overall Survival

Overall survival is defined as the time from the date of randomization to the date of death. All deaths during the study will be considered as OS events.

Subjects who were lost to follow-up or withdrew consent will be censored at the date the subject was last known to be alive. Subjects who are still alive at the clinical cut-off date will be censored at the date of data cutoff.

Determination of date of OS event or censoring is summarized in Table 6 below.

Table 6 OS Event and Censoring Method

Situation	Date of Event or Censoring	Outcome
Death during study	Date of death	OS Event
Death after data cut-off	Date of data cut-off	Censored
Subject still alive at data cut-off	Date of data cut-off	Censored
Subject lost to follow-up or withdrawal of consent before data cut-off	Date of last known to be alive	Censored

The analysis of OS will be performed on the Per-Protocol Analysis Set 1 as the primary analysis set. The median OS and the OS rates at 12, 18, and 24 months will be estimated using the Kaplan–Meier method and presented with 2-sided 95% CIs. The hazard ratio of lenvatinib 14 mg over lenvatinib 18 mg and the corresponding 90% CIs will be estimated using the Cox regression model with Efron's method for ties, stratified by MSKCC prognostic group and prior PD-1/PD-L1 treatment. The Kaplan-Meier curve of OS will also be plotted over time for each treatment arm.

Sensitivity analyses of OS based on the Per-Protocol Analysis Set 2 and Full Analysis Set will be performed in a similar manner as described above.

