9.1.2.2 Follow-Up Period

The Follow-Up Period will begin immediately after the off-treatment assessments have been completed and will continue as long as the study subject is alive, until the study subject withdraws consent, or until the data cutoff for the primary analysis. Subjects who discontinue study treatment before disease progression will continue to undergo tumor assessments every 8 weeks and as of Amendment 06, send these to the imaging core laboratory (ICL) until documentation of disease progression or start of another anticancer therapy. Following the Off-Treatment Visit, subjects will continue to be followed every 12 weeks (± 1 week) for survival and PFS2, and all anticancer treatments received will be recorded until the data cutoff for the primary analysis. This information will be recorded unless the information is not allowed to be provided due to confidentiality.

If a subject discontinues study treatment and does not consent to continued follow-up, the investigator must not access confidential records that require the subject's consent. However, an investigator may consult public records to establish survival status. Copies of tumor assessment scans will no longer be sent to the ICL and independent review will not be carried out during the Follow-Up Period.

All subjects who are still on study treatment following the data cutoff for the primary analysis (ie, at the end of the Randomization Phase) will continue to receive the same study treatment. Tumor assessments will be performed according to the local standard of care, but not less frequently than every 12 weeks or earlier if clinically indicated, and scans will no longer be required to be sent to the ICL. Subjects will continue to receive study treatment until confirmed disease progression, development of unacceptable toxicity, subject request, withdrawal of consent, lost to follow up or study termination by the sponsor. If the study is terminated by the sponsor, study drug (s) will be provided to subjects where commercial access is not available.

The Off-Treatment Visit will occur within 28 days after the final dose of study treatment. All AEs and SAEs will be captured up to 28 days after last dose of study drug (Table 7).

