9.7.1.1.2 SECONDARY ENDPOINTS

- Progression-free survival (PFS), defined as the time from the date of randomization to the date of first documentation of disease progression or date of death or the date of data cutoff for the primary analysis, whichever occurs first. PFS censoring rules will be defined in the statistical analysis plan (SAP) and will follow FDA guidance.
- ORR as assessed by the investigator according to RECIST 1.1 at the end of treatment. ORR is defined as the proportion of subjects with BOR of CR or PR at the end of treatment. To be considered BOR, all responses must be confirmed no less than 4 weeks after the initial assessment of response.
- Overall safety profile and tolerability of lenvatinib in combination with everolimus.
- Proportion of subjects who discontinue treatment due to toxicity, defined as the proportion of subjects who discontinue study treatment due to TEAEs.

- Time to treatment failure due to toxicity, defined as the time from the date of randomization to the date that a subject discontinues study treatment due to TEAEs.
- Lenvatinib and everolimus exposure parameters and PK and PD drug-drug interactions.
- Overall survival (OS), measured from the date of randomization until date of death from any cause. In the absence of confirmation of death, subjects will be censored either at the date that the subject was last known to be alive or the date of data cutoff for the primary analysis, whichever comes earlier.
- Health-Related Quality of Life (HRQoL) will be assessed using the Functional Assessment of Cancer Therapy-Kidney Symptom Index-Disease Related Symptoms (FKSI-DRS), the European Organization for the Research and Treatment of Cancer (EORTC) QLQ-C30 and the European Quality of Life (EuroQol) EQ-5D-3L instruments.
- PFS2, defined as the time from randomization to the date of disease progression after next line of therapy or death from any cause or the date of data cutoff for the primary analysis, whichever occurs first. PFS2 censoring rules will be defined in the SAP.

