5.1.2 Secondary Endpoints

The secondary efficacy endpoints are defined as follows:

- PFS, defined as the time from the date of randomization to the date of first documentation of disease progression or date of death, whichever occurs first.
- ORR as assessed by investigator according to RECIST 1.1, defined as the proportion of subjects with BOR of CR or PR during treatment or within 28 days after the last dose date but on or prior to the start of new anticancer therapy. To be considered as BOR, all responses must be confirmed no less than 4 weeks after the initial assessment of response.

- Overall safety profile and tolerability of lenvatinib in combination with everolimus.
- Proportion of subjects who discontinue treatment due to toxicity, defined as the proportion of subjects who discontinue study treatment due to TEAEs.
- Time to treatment failure due to toxicity, defined as the time from the date of randomization to the date that a subject discontinues study treatment due to TEAEs.
- Lenvatinib and everolimus exposure parameters and PK and PD drug-drug interactions.
- OS, measured from the date of randomization until date of death. In the absence of confirmation of death, subjects will be censored either at the date that the subject was last known to be alive or the date of data cutoff, whichever comes earlier.
- HRQoL will be assessed using the FKSI-DRS, the EORTC QLQ-C30 and the EuroQol EQ-5D-3L instruments.
- PFS2, defined as the time from randomization to the date of disease progression on next line of therapy or death, whichever occurs first.

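### The overall-survival censoring rule in SAP 5.4.2.3 and Table 6 conflicts with SAP 5.1.2 and the protocol for subjects in active follow-up who were last contacted before the data cutoff

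*SAP*

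**What the plan says.** The plan states the OS censoring rule in three places.

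- **Protocol 9.7.1.1.2** (repeated in the synopsis): without confirmation of death, the censoring date is "the date that the subject was last known to be alive or the date of data cutoff for the primary analysis, whichever comes earlier".
- **SAP 5.1.2**: the same rule. Subjects are "censored either at the date that the subject was last known to be alive or the date of data cutoff, whichever comes earlier".
- **SAP 5.4.2.3 and Table 6**: the living are split into two groups. The row "Subject lost to follow-up or withdrawal of consent before data cut-off" takes the date last known alive. The row "Subject still alive at data cut-off" takes the cutoff date, as does a death after the cutoff. The text says the same: "Subjects who are still alive at the clinical cut-off date will be censored at the date of data cutoff".

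The SAP does not define what establishes that a subject is still alive at the cutoff. SAP section 7 declares no changes to the planned analyses, so the difference is not presented as deliberate.

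On data collection, protocol 9.1.2.2 says that after the Off-Treatment Visit "subjects will continue to be followed every 12 weeks" (±1 week) for survival and PFS2, until the data cutoff for the primary analysis.

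**The concern.** Take a subject who is off treatment, neither lost nor withdrawn, has no recorded death, and was last contacted some weeks before the cutoff. This is an ordinary case under 12-weekly contact. Table 6 has no row for it except the still-alive row, which gives the cutoff date. SAP 5.1.2 and the protocol give the date of last contact. A programmer has to choose, and the choice changes the output.

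The adjacent PFS2 rule (SAP 5.4.2.4) goes the other way: a subject with no new anticancer therapy and no documented death is censored at the date last known alive. OS and PFS2 use the same follow-up, so one subject can be credited with survival to two different dates.

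At stake are the OS median, the 12-, 18- and 24-month rates and their confidence intervals, which are planned outputs. Crediting time during which a death would not have been recorded adds person-time without the matching events, and so pushes the curve up, most at the late time points.

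**Working it through.** The documents state no OS figure (median, event count or power), so there is nothing to reproduce. The check compares the rules case by case and then sizes the difference by simulation.

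**Step 1. Censoring date under each rule, for a subject with no death on or before the cutoff**

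| Subject | SAP 5.1.2 and protocol | SAP 5.4.2.3 / Table 6 | Same? |
|---|---|---|---|
| Confirmed alive on or after cutoff | cutoff | cutoff | yes |
| Died after cutoff | cutoff | cutoff | yes |
| Lost or withdrawn before cutoff | last known alive | last known alive | yes |
| Active follow-up, last contact before cutoff | last known alive | cutoff (only the still-alive row fits) | **no** |

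**Step 2. Time credited.** Added time = cutoff − last contact. With contact every 12 ± 1 weeks the maximum is 12 + 1 = 13 weeks. If the contact phase is random, the mean over a 12-week interval is 12 / 2 = 6 weeks, or 6 / 4.345 = 1.38 months. As a rough guide, for an assumed median OS of 20 months the monthly hazard is ln 2 / 20 = 0.0347. The chance that a subject alive at last contact dies in the gap is then about 1 − exp(−0.0347 × 1.38) = 4.7%.

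**Step 3. Effect on the Kaplan–Meier estimate.**

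From the documents: 306 subjects in Per-Protocol Analysis Set 1, 12-weekly contact off treatment, 28-day cycles on treatment. The cutoff is placed 24 weeks (5.5 months) after the last entry.

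Assumed, because the documents do not give them: exponential OS with median 15–30 months; uniform accrual over 20 or 24 months; last contact uniform over the contact interval; and, where used, a median of 9 months on treatment with 4-weekly contact during it.

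*Deaths after last contact not recorded.* Overstatement under cutoff censoring, in percentage points, over medians of 15–30 months:

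| Accrual | Contact | 12 mo | 18 mo | 24 mo |
|---|---|---|---|---|
| 20 mo | 12-weekly for all | 1.1–1.7 | 2.3–3.1 | 4.9–6.0 |
| 20 mo | 4-weekly on treatment | 0.7–1.1 | 1.6–2.3 | 4.1–5.0 |
| 24 mo | 12-weekly for all | 0.9–1.4 | 1.6–2.4 | 2.9–3.5 |
| 24 mo | 4-weekly on treatment | 0.6–0.9 | 1.3–1.7 | 2.3–2.8 |

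The rounded ranges 0.7–1.6, 1.4–3 and 2.5–6 cover this grid to within 0.2 point. Last-known-alive censoring stays within about 0.2 point of full ascertainment throughout. With 24-month accrual and a 12–13 week gap, the estimated median rises by about 0.9 month when the true median is 15, and by 1.5–1.7 months when it is 20. About 6–7% of deaths before the cutoff go unrecorded.

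*All deaths up to the cutoff recorded.* Cutoff censoring is unbiased. Last-known-alive censoring, with alive status not updated, is then the biased rule: it lowers the 24-month rate by about 2.4–3.4 points with 24-month accrual and a 12-week gap.

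*Alive status confirmed at the cutoff for everyone.* Both rules give the same date and the difference is zero.

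**The case against.** The strongest reply is that the still-alive row means known to be alive at the cutoff. On that reading the earlier of the two dates is the cutoff, and all three places agree. There is support for it:

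- SAP 5.2.2 plans a summary of each subject's status at the cutoff, in categories close to those of Table 6.
- The row for deaths after the cutoff presupposes some later information.
- Subjects still on treatment continue visits after the cutoff (protocol Table 7).
- Public records may be consulted for survival status when follow-up is refused.
- Deaths within 28 days of the last dose are reportable as serious adverse events.
- SAP section 9 places derivation rules in separate documents.

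This narrows the point but does not remove it. A status summary does not say how or when status is obtained. The public-records provision is optional and concerns subjects who do not consent to further follow-up. For off-treatment subjects, contact ends at the cutoff and no update is described. Table 6 still has no row for the subject last contacted before the cutoff.

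Three stronger readings are tempting, and the documents do not support them.

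- **That Table 6 contradicts the protocol for every living subject.** Three of the four cases in Step 1 agree.
- **That the rule inflates OS.** It does so only if deaths in the gap go unrecorded. With complete death capture the bias lies with the other rule. The documents establish neither state.
- **That 5–6 points at 24 months is the expected size.** That figure needs 20-month accrual and 12-weekly contact for everyone, including subjects seen every 28 days. It also falls where only about 8–13 of 306 simulated subjects remain at risk.

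**Conclusion.** The inconsistency stands for one class of subject: in active follow-up, no recorded death, last contact before the cutoff. For them the SAP gives two dates up to about 12–13 weeks apart, and the one in the analysis section departs from the protocol definition without being declared as a change.

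The size is conditional. If deaths in the gap are missed, OS is overstated by roughly 0.7–1.6, 1.4–3 and 2.5–6 points at 12, 18 and 24 months. Those figures rest on assumed accrual, median OS and contact pattern, and accrual dominates the 24-month figure. If all deaths are captured, cutoff censoring introduces no bias.

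The consequence is limited. OS is descriptive, and SAP 5.3.3 plans no formal tests on secondary efficacy endpoints. The ORR non-inferiority decision, its error rates and the safety test are untouched. A reader might infer that the hazard ratio is distorted, but both arms share one rule and one contact schedule, and nothing in the documents points to a differential effect. The correction is still worth making, because it is cheap and removes a stated rule that can give a wrong result.

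**What to change.** Amend SAP 5.4.2.3 and Table 6 so that any subject without a death on or before the data cutoff is censored at the earlier of the date last known alive and the cutoff. The cutoff date is then used only when contact on or after the cutoff confirms survival. In Table 6, replace the still-alive row with one for subjects confirmed alive on or after the cutoff, and add one for subjects whose last contact precedes it. Define which records count towards the date last known alive.

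Also state whether survival status is updated for all subjects at the cutoff. This matters because last-known-alive censoring is itself biased downward if deaths are captured up to the cutoff but living subjects' status is not refreshed. With a complete update the two rules coincide.

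The text change is about one sentence and one or two table rows, plus the statement on status updates, and it restores the protocol's own definition. The downside is slightly shorter reported follow-up.
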